I. An *in vivo* clinical trial was approved by CCHMC IRB and was completed in the Cincinnati Children's Hospital Human Performance Laboratory and Radiology Department (Study ID: 2015-2205; PI: [name]). We sought to (1) identify brain networks in performance of a cognitive task, (2) evaluate whether longitudinal changes in performance are associated with alterations in brain network connectivity after a season of head contact competitive play, and (3) determine the effect of a jugular vein compression device on these relationships. Male high school football athletes were assigned to a collar (N=12, age=16.4±1.2) or non-collar group (N=13, age=16.2±1.6). Subject response times (RT) during a visual go/no-go test were recorded before and after the season. Neuroimaging data were acquired prospectively pre and post season. Functional networks were parcellated from preseason data via independent component analysis and intersected with the Harvard-Oxford brain atlas to form regions of interest. For all subjects at preseason, RT were positively correlated with connectivity within the salience network (r=0.47, p=0.003) but not any other network (p>0.05). Consequently, we evaluated associations between longitudinal changes in RT and connectivity within this network for each group; changes in RT were positively correlated with changes in connectivity for the non-collar group (r=0.58, p=0.038) but not the collar group (r=0.38, p=0.221). The salience network was associated with RT in a visual go/no-go task, consistent with its central role in motivation and a readiness to act. Associations between altered RT and network connectivity for only the non-collar group suggests not only that

exposure to head impacts may affect critical processing within the salience network, but that the collar may afford a protective effect in stabilizing brain network connectivity.

(4) STUDY DESIGN:

All testing will be performed in the SPORT Center, Division of Sports Medicine at Cincinnati Children's Hospital. Ultrasound testing will consist of measurement of dilation and compression of the jugular veins following the application of a generic jugular vein compression device. The ultrasound testing will be completed in 20 minutes or less.

(5) DURATION:

Each participant will participate in 1 planned study visit that may take up to 20 minutes. Data analysis will continue for a 6 month period following the final enrollment.

(6) SELECTION & RECRUITMENT OF PARTICIPANTS

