Once a participant is identified as a potential participant, is contacted by a CCHMC/Sports Medicine representative and verbally agrees to participate, the process to obtain consent will begin. The study coordinator will review the informed consent and the participant will have an opportunity to ask any questions regarding the study and/or the study protocol. At that time, the participant will be given time to decide whether or not they wish to participate and if so, asked to sign the informed consent. Once the signature is obtained, the participant will be given a copy of the consent and testing will commence. At no time will the participant be coerced into participation. Receiving the informed consent prior to enrollment will allow the participants to review the study information prior to participation in the study. This will aid the participant to make an informed, unforced decision regarding election to participate in the study.

The participants will be given adequate time to review the study materials and ask questions. If they choose to participate, the patient and parent will sign the IRB approved consent/assent forms. It will be made clear to the patient and their parents that participation in the study is voluntary. Subjects over the age of 18 will complete the Adult Subject Consent Form.

In the event that a parent or guardian will not be present at the scheduled testing appointment, consent/assent forms will be provided ahead of time for review. The coordinator will ensure that all necessary forms have been signed prior to any data collection.

(8) STUDY PROCEDURES

Ultrasound Testing

The study coordinator will be responsible for providing the appropriate sized collar based on measured neck circumference. At first fitting of the collar a registered vascular technologist will utilize ultrasound to ensure that the collar fits correctly and is activated as prescribed. Baseline measures with standard collar will be measured and recorded via ultrasound video following the methods described below.

Baseline ultra-sound imaging-Standard collar

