Sitting upright, and facing forward, ultra-sound coupling gel is applied to the lateral neck, and the right side common carotid artery, and IJV in the transverse plane, are identified to verify normal anatomy. Collar positions will be marked on the neck using stickers or other temporary marking methods. The collar is then placed into proper position on the study volunteer's neck. To further evaluate responsiveness to the collar, a 15 s video clip is obtained, recording the collar in its proper position, the collar opened away from the neck, and the collar returned to its proper position. The largest transverse dimension at initial collar placement, and the smallest transverse dimension at opened collar view and again at proper collar replacement, will be used for IJV metrics.

IJV Compression ultra-sound imaging

With proper placement of IJV compression collar confirmed, pressure is increased in small intervals of pressure unilaterally until IJV compression is visually observed. The collar will then be rotated radially anterior and posterior to its initial position around the IJV. This process will be repeated at .2 increments of pressure until the 1.5 lbs pressure of the standard collar is achieved. The ultrasound technologist will record the jugular vein measurements relative to each indicated pressure level.

(9) DATA ANALYSIS/METHODS:

Data Storage.

The personal demographic data for each participant will be blinded from the researchers, and a coded identification number will be used to track all collected data. Data will be stored on password-protected computers and only pertinent research personnel will have access. Data forms will be stored by coded identification number in a locked cabinet to which only pertinent research personnel have access. All data will be collected for research purposes only.

Statistical analyses will be performed with SPSS statistical software (SPSS Inc, Chicago IL). Data regarding the descriptive information (such as mean and standard deviation) will be calculated for demographic, anthropometric and ultrasound variables of interest. Sex and age specific analysis will be compared between the test conditions (baseline vs. X pressure) using a paired student T-test.

(10) FACILITIES AND PERFORMANCE SITES:

All ultrasound testing will be performed in the SPORT Center in the Division of Sports Medicine.

(11) POTENTIAL BENEFITS:

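### The standard-collar clip takes the largest vein dimension at first placement but the smallest with the collar open, so initial-on minus open is biased upwards

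*Combined protocol and SAP*

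**What the plan says.** Section 8 introduces the standard-collar recording in these words: "To further evaluate responsiveness to the collar, a 15 s video clip is obtained". The clip has three phases, "recording the collar in its proper position, the collar opened away from the neck, and the collar returned to its proper position". The dimensions taken from it are "The largest transverse dimension at initial collar placement, and the smallest transverse dimension at opened collar view and again at proper collar replacement". They feed a set of jugular vein metrics for which no formula is given.

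Four other statements bear on the point:

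- Section 4 (Study Design) describes the testing as "measurement of dilation and compression of the jugular veins following the application of a generic jugular vein compression device", so the vein may be found wider or narrower.
- Section 8 (Ultrasound Testing) treats the standard-collar readings as the baseline: "Baseline measures with standard collar will be measured and recorded via ultrasound video following the methods described below".
- Section 8 (IJV Compression ultra-sound imaging) says of the stepped-pressure part: "The ultrasound technologist will record the jugular vein measurements relative to each indicated pressure level". It gives no rule for choosing a largest, smallest or average value.
- Section 9 plans the comparison: "Sex and age specific analysis will be compared between the test conditions (baseline vs. X pressure) using a paired student T-test". It does not say which reading is the baseline.

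No section sets a common reading rule for the three collar states, ties the readings to the breathing or cardiac cycle, fixes the number of frames, or explains why opposite extremes are used.

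**The concern.** The clip exists to show how the vein responds to the collar, and the natural contrast for that is collar-on against collar-open. Under the stated rule, the first collar-on view is summarised by its largest value and the open view by its smallest. Vein size on ultrasound can vary within a view through breathing, pulse, probe pressure and reading error. Any such variation enters the difference as apparent collar response.

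Read literally, the rule also summarises the same collar-on state twice by opposite extremes: the maximum at first placement and the minimum at replacement. The second value would then fall below the first even if the vein behaved identically.

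Three things are at stake:

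- The error points the same way as the dilation above the collar that the background section reports from the earlier football study, so it could pass as confirmation.
- A true narrowing would be reduced or hidden.
- If within-view variation differs by age or sex, the bias differs too and would appear as a group difference, in a study designed to compare those groups.

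**Working it through.** The plan gives no figure on this point, so there is none to reproduce. The check asks what the stated rule yields when the collar has no effect.

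**Inputs from the protocol.** Maximum at first placement; minimum with the collar open; minimum at replacement (literal reading); one 15 s clip covering three phases (section 8). About 100 participants, divided equally by sex (section 6).

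**Assumptions, not in the documents.** Normal readings with the same within-view standard deviation σ in every view; k readings per view; separate views independent of each other; successive readings within a view either independent or with first-order autocorrelation ρ.

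**Formula.** Let E_k be the expected maximum of k standard normal readings. By symmetry the expected minimum is −E_k. With no collar effect:

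- initial-on minus open = E_k σ − (−E_k σ) = 2 E_k σ
- initial-on minus replaced-on = 2 E_k σ
- replaced-on minus open = −E_k σ − (−E_k σ) = 0
- initial-on minus the mean of another view = E_k σ

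**Independent readings.** Numerical integration gives E_2 = 0.564, E_5 = 1.163 and E_10 = 1.539. Doubling gives 1.128, 2.326 and 3.078 σ.

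**Correlated readings.** 200,000 simulated pairs of views per setting.

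| False initial-on minus open, in σ | k = 2 | k = 5 | k = 10 |
|---|---|---|---|
| Independent | 1.1 | 2.3 | 3.1 |
| ρ = 0.5 | 0.8 | 1.9 | 2.7 |
| ρ = 0.9 | 0.4 | 1.0 | 1.6 |
| Same extreme in both views, any ρ | 0.0 | 0.0 | 0.0 |

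With five readings, a true narrowing of 2.3 σ (independent) or 1.0 σ (ρ = 0.9) would read as zero on average.

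**As a share of vein size.** If σ were 5%, 10% or 20% of mean size (assumed), the false difference with five independent readings would be 2.326 × 5% = 12%, 2.326 × 10% = 23% or 2.326 × 20% = 47%.

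**Short views.** Three states in 15 s leave at most 15 / 3 = 5 s each if time is shared equally. For a sinusoidal variation at an assumed 12 to 20 cycles per minute, sampled at 10 frames per second with random phase, maximum minus minimum averages about 0.9 to 1.0, 1.6 to 1.7, 1.9 and 2.0 times the amplitude for views of 1, 2, 3 and 5 s. Short views reduce the bias but do not remove it.

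**Effect on a test.** Suppose a paired t-test at two-sided 0.05 (assumed) compared initial-on with open, with 2 to 10 independent readings per view. Allow a zero-mean difference between views that varies across participants with a standard deviation of up to 3 σ. With no average collar effect, the test rejects in 93% to 100% of simulated studies at n = 100 and in 68% to 100% at n = 50 (one sex). With the same extreme in both views, rejection stays near 5% (4.5% to 6.1%).

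**The planned baseline against pressure test.** If the baseline were the initial-on maximum and the pressure readings were means (assumed), the false difference would be E_k σ: 0.6, 1.2 or 1.5 σ for independent readings and 0.2, 0.5 or 0.8 σ for ρ = 0.9.

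**The case against.** The strongest reply is that the protocol never writes initial-on minus open as its metric. On the literal reading the clip also supplies a fair pair, replaced-on against open. The only named test is baseline against pressure, which this error reaches only if the baseline is one of these extremes and the pressure readings use another statistic. This limits the scope, and the conclusion is worded accordingly. It does not clear the plan: section 8 states opposite rules for the two views that a reader would compare, and nothing directs the analyst to the fair pair.

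The wording can also be read in other ways. If the largest dimension is meant to be repeated at replacement, the mismatch between the two collar-on values disappears, but replaced-on against open then becomes maximum against minimum as well. If largest and smallest refer to axes of the cross-section and not to extremes over time, the figures above do not describe the error, but the two views are still measured differently.

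The size is assumed throughout, and adjacent frames in a view of about 5 s are unlikely to be independent. That stands: the correlated rows may be nearer the truth, and all rows show direction and range, not an expected value. A common offset would also largely cancel in comparisons between sexes or ages if within-view variation is similar across groups. The documents do not show whether it is.

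**Conclusion.** The concern holds and should be fixed. If largest and smallest mean extremes over the clip, any standard-collar response built from initial-on against open is biased upwards. The direction is certain unless the dimension does not vary within a view or only one frame is read. The size runs from 0.4 to 3.1 within-view standard deviations over 2 to 10 readings and correlations from 0 to 0.9, assuming normal readings with equal variation in each view. It cannot be put in millimetres or per cent from the documents. On the literal reading, the two collar-on values differ by the same amount with no real change, while replaced-on against open is like for like. Whether the section 9 paired t-test is affected cannot be settled, because the plan defines neither its baseline nor the statistic used at each pressure level.

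**What to change.** In section 8, use one statistic on one named axis for all three collar states. This can be the mean, or the same extreme, over a fixed period or number of cycles while the collar is still. Define the response as collar-on minus collar-open under that rule, and treat the replaced-collar value as a repeat of the first collar-on value. Apply the same statistic at each pressure level and collar rotation. In section 9, name the value that serves as baseline in the paired t-test.

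The mean also copes with views whose variation or length differs; the same extreme cancels only when these are similar. At an assumed 12 to 20 breaths per minute, 5 s holds only 5 × 12 / 60 = 1.0 to 5 × 20 / 60 = 1.7 breaths. A mean over several breathing cycles would therefore need longer clips within the 20-minute visit, whereas the same-extreme rule can be applied to the 15 s clips as planned.

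The cost is one or two sentences in section 8, a phrase in section 9 and some extra reading time per view. Standard-collar clips can be re-read afterwards. The plan describes no video at the pressure levels, so the rule must be set before those readings are taken, or short clips saved there too. The change concerns measurement only and alters no applied pressure or clinical procedure.

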A landmark article, published in the *Journal of Neurosurgery*, used a standard acceleration-deceleration impact laboratory model of mild TBI. The study showed a successful and marked reduction of axonal injury following Internal Jugular Vein (IJV) compression as indicated by immunohistochemical staining of Amyloid Precursor Proteins (APP) (Smith, Bailes et al. 2012, Turner, Naser et al. 2012). It is argued that IJV compression reduces slush-mediated brain injury by increasing intracranial blood volume and reducing the compliance and potential for brain movement within the confines of the skull. The potential for such technique to mitigate both linear and rotational brain injury in humans by “internal protection” represents the most novel approach to mitigating TBI. Initial safety testing and early (pre) clinical trials (detailed below) indicate that the collar application is both safe and efficacious to prevent brain microstructure and neurophysiological changes in response to head impacts. These data create the impetus better understand the jugular vein’s response to collar application. Relative to the proposed investigation we have compared the ultrasound response to the standard collar in high school female and male athletes and have not seen a sex specific response. We are interested to learn more about the relative responsive of different ages and sex to the collar application and to determine the minimum relative pressure that is required to invoke the jugular vein response.

Summary of Prior Work

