We aim to recruit approximately 100 healthy volunteers divided equally between the sexes. The normal, healthy participants (age 7-60 years old) will be recruited from local school districts local sports clubs and teams, local colleges, adult sport leagues, and professional sports teams, through our well established network with area coaches and athletic trainers. To obtain the various age groups we will also recruit from that we may recruit from colleagues and staff members. All recruited participants will be made aware that participation is voluntary and will not be held against them if they decide not to participate. Questions regarding participation will be answered during the presentations or through e-mail or phone. Participants will be contacted via telephone to further explain the study, answer any additional questions and to enroll them in the study. The participants and parents/guardians (if subject under age of 18) who voluntarily agree to participate will be scheduled to complete the pre-participation testing. The participant and parent/guardian (if subject under the age of 18) will read and sign the "Consent to Participate in a Research Study" form, approved by the Institutional Review Board of Cincinnati Children's Hospital. If the participant and parent/guardian does not read or sign the form, they will not participate in the study. Additional Adult volunteers will be recruited via word of mouth or through affiliations with the teams/clubs noted above, through personal contacts, or through emails sent via Clinical Studies.

Inclusion criteria

- Normal healthy volunteer aged 7-60
- Able to provide written consent
- Able to tolerate hypercapnia for 1-2 minutes

Exclusion criteria

- Unable to provide written consent
- History of neurological deficits, previous cerebral infarction, or severe head trauma as indicated through pre-season screening:
- Medical contraindications to restriction of venous outflow via the internal jugular veins (known increased intracerebral pressure, metabolic acidosis or alkalosis)
- Glaucoma (Narrow Angle or Normal Tension)
- Hydrocephalus
- Recent penetrating brain trauma (within 6 months)

- Known carotid hypersensitivity
- Known increased intracranial pressure
- Central vein thrombosis
- Any known airway obstruction
- Any known seizure disorder

(7) PROCESS OF OBTAINING CONSENT

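### The only planned test compares pressures within a sex or age group, so nothing in the plan estimates or tests whether the jugular response differs by sex or age

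*Combined protocol and SAP*

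**What the plan says.** The title concerns ultrasound response by sex and age, and Section (2) PURPOSE sets out to measure the jugular response to several pressures across ages and gender. Section (3) BACKGROUND reports that "we have compared the ultrasound response to the standard collar in high school female and male athletes and have not seen a sex specific response" and continues: "We are interested to learn more about the relative responsive of different ages and sex to the collar application". The same sentence adds a second aim, finding the minimum pressure that produces a response. Section (6) says "We aim to recruit approximately 100 healthy volunteers divided equally between the sexes", with ages from 7 to 60. It mentions age groups but gives no cut-points or group sizes.

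Section (9) DATA ANALYSIS/METHODS plans descriptive statistics, such as means and SDs, and one test: "Sex and age specific analysis will be compared between the test conditions (baseline vs. X pressure) using a paired student T-test".

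The baseline for that test is described in two ways. Section (8) first says "Baseline measures with standard collar will be measured and recorded via ultrasound video". The clip taken under the baseline heading, however, records the vein with the collar in place, opened and replaced, and "the smallest transverse dimension at opened collar view and again at proper collar replacement, will be used for IJV metrics". Pressure is then stepped up "until the 1.5 lbs pressure of the standard collar is achieved".

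**The concern.** The plan does not supply the comparison that the study was set up to make. Baseline versus pressure is a contrast within a person, while sex and age vary between people. Running the paired test separately in each sex or age group answers whether the vein changed in that group. It does not answer whether it changed more in one group than in another.

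The study could therefore finish without an estimate or interval for the sex or age difference. Readers would probably set the subgroup p-values side by side, which can mislead in two ways. Groups with the same true response can fall on opposite sides of 0.05, and a real difference can go unseen when every group responds clearly.

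The undefined baseline adds to this, because the change score itself is not fixed. If the baseline is the standard collar, the last step (1.5 lbs) compares the same nominal pressure with itself.

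**Working it through.** **Reading check.** No section contains a two-sample test, ANOVA, regression, interaction term or mixed model. Section (15) says that results will be summarised by age, but that is a privacy statement and names no comparison. The documents give no alpha, power, effect size or SD, so there is no stated calculation to reproduce.

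**Inputs.** From Section (6): about 100 participants split equally, taken as 50 per sex, and ages 7 to 60. Assumed: two-sided alpha 0.05, normally distributed changes with equal SD, and effects in units of the SD of within-person change. Figures are for one pressure level without multiplicity adjustment.

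**1. Same true response in both sexes.** The paired power p at n = 50 comes from the noncentral t distribution with 49 df and noncentrality d√50. The chance that exactly one sex is significant is 2p(1 − p).

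| True change d (SD) | p | 2p(1 − p) |
|---|---|---|
| 0.2 | 0.284 | 0.41 |
| 0.28 | 0.493 | 0.50 |
| 0.4 | 0.792 | 0.33 |
| 0.5 | 0.934 | 0.12 |
| 0.6 | 0.986 | 0.03 |
| 0.8 | 0.9998 | about 0 |

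**2. Different true responses, 0.6 and 1.2 SD.** Both paired tests are significant with probability 0.986 × 1.000 = 0.986. A two-sample comparison of the changes (difference 0.6 SD, 50 v 50, 98 df) has power 0.844.

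**3. What a direct sex comparison would give.** The 95% CI half-width is 1.984 × √(2/50) = 0.397 SD. The difference detectable with 80% power is 0.566 SD.

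**4. Age in bands.** The documents define no bands, so assume four of 25 with the same true response. The chance that some bands are significant and others are not is 1 − p⁴ − (1 − p)⁴.

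| True change d (SD) | p (n = 25) | Mixed result |
|---|---|---|
| 0.28 | 0.270 | 0.71 |
| 0.4 | 0.484 | 0.87 |
| 0.5 | 0.670 | 0.79 |
| 0.6 | 0.821 | 0.55 |
| 0.8 | 0.970 | 0.12 |

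**5. Age as a continuous variable.** With n = 100 and adjustment for sex, 80% power is reached at a partial correlation of 0.272. If ages are spread evenly over 7 to 60, their SD is 53/√12 = 15.3 years, and 0.272 × 10/15.3 ≈ 0.18 SD of change per 10 years.

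**The case against.** The paired tests are not pointless. Section (3) also seeks the minimum pressure that produces a response, and baseline versus each pressure bears directly on that. That stands, and it is why the tests should stay.

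Sex-specific paired analyses would also yield a mean change, SD and n per group, from which a difference and its interval could be worked out afterwards. That is true, but the plan commits to no such contrast. For age it cannot be done as written, because no groups are defined.

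The high discordance figures need small effects. Pressure is raised until compression is seen, and Section (3) cites a consistent dilation response in an earlier football study, so changes may be large at the higher pressures. This also stands: with two sexes the risk of discordance is 3% at 0.6 SD and near zero from 0.8 SD. But with large responses every group is significant, and the opposite failure, a masked difference, becomes the main one.

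Finally, this is a single visit of up to 20 minutes in healthy volunteers, with no formal hypothesis, and the omission can be repaired before analysis. That makes the repair easy. It does not make the planned test suited to the question in the title.

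**Conclusion.** The concern holds. It follows from the wording of Section (9) and from what a paired test can measure, and depends on no calculation. No between-group estimate, interval or test for sex or age is planned, although this is a main study question. Because the gap concerns that question, it must be fixed before analysis.

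The numerical consequences rest on assumed alpha, effect sizes, equal SDs and group sizes. For the two sexes, false discordance ranges from 50% to nearly nil across the effects considered. When both sexes respond clearly, the larger danger is that a difference as big as 0.6 SD passes unnoticed. The inconsistent description of the baseline is a secondary defect, but it must be settled before any change score can be computed.

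**What to change.** Keep the paired t-tests for whether the vein changes at a given pressure within a group, and add to Section (9):

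> At each pressure level, each participant's change from baseline will be regressed on sex and continuous age. The sex and age coefficients will be reported with 95% confidence intervals. Conclusions about sex or age differences will rest on these coefficients at the pre-named primary pressure level, not on subgroup p-values.

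The text should also state:

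- **Baseline:** whether it is the open-collar or the standard-collar measurement. The passages in Section (8) need to be reconciled.
- **Primary level:** one pressure level for the analysis, and which collar position supplies the measurement, since the collar is rotated at each step. Report n at every level, because the level at which compression is first seen may differ between participants.
- **Change scale:** one that stays defined if a vein collapses to zero, such as the difference, or percent change from open-collar size where that size is not zero.
- **Age:** a check that the relation is roughly linear over 7 to 60 years.

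If all levels are modelled together, use a mixed model with a participant random intercept and random pressure slope, and report the sex and age main effects as well as their interactions with pressure. Neck circumference can enter a secondary model, since Section (8) already calls for an "appropriate sized collar based on measured neck circumference".

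The cost is analysis wording, a little more model checking, and naming a baseline and a primary level in advance. No participants, visits or measurements are added, and linear regression is available in the named software.

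### Section (9) tests change within age bands that are never defined, so the question of whether the response differs by age has no valid test

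*Combined protocol and SAP*

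**What the plan says.** Age is a stated object of the study. It is in the title and in section (2), and section (3) puts the interest in comparative terms: "We are interested to learn more about the relative responsive of different ages and sex to the collar application".

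Section (6) sets the sample: "We aim to recruit approximately 100 healthy volunteers divided equally between the sexes". It gives age only as a range, "Normal healthy volunteer aged 7-60". The same section refers to groups in passing ("To obtain the various age groups we will also recruit from") but gives no number of groups, boundaries or quotas.

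Section (9) promises descriptive statistics ("Data regarding the descriptive information (such as mean and standard deviation) will be calculated for demographic, anthropometric and ultrasound variables of interest") and then one inferential method: "Sex and age specific analysis will be compared between the test conditions (baseline vs. X pressure) using a paired student T-test". It gives no comparison between ages, no regression on age, no significance level and no rule for multiple tests. Section (8) repeats the measurement in steps of 0.2 up to 1.5 lbs, so X stands for several pressures.

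**The concern.** The paired t-test compares two measurements on the same people and has no place for a covariate. To make it age specific, participants aged 7 to 60 must be sorted into bands and the test run in each. Two problems follow.

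First, the test answers a different question. It asks whether the mean change is zero within a band; the study asks whether the change differs between ages. With only within-band results to report, the natural step is to note which bands are significant and read that as an age effect. That reading is invalid, because significance in a band depends on its size and on chance as well as on its true change.

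Second, the bands are open. Nothing in the documents fixes where they fall, and a between-band comparison added later would discard age information within each band.

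At stake is whether the study can support a statement about age in either direction.

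**Working it through.** **Inputs from the documents.** About 100 participants, about 50 per sex, ages 7 to 60 (section 6); within-group paired tests only (section 9). No alpha, power, SD or effect size is given, so the target of 100 cannot be reproduced.

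**Assumptions not in the documents.** N = 100 with no dropout, two-sided alpha 0.05, normal responses, ages uniform over 7 to 60, and a correlation r of 0.30 between age and change unless stated otherwise.

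**Step 1: the test as planned.** The power of a paired t-test with n people and standardised change d comes from the noncentral t with n − 1 degrees of freedom and noncentrality d√n.

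- The change detectable with 80% power is 0.28 SD at n = 100, 0.40 SD at n = 50 and 0.58 SD at n = 25.
- Suppose four age bands of 25 share the same true change, d = 0.4. The noncentrality is 0.4 × √25 = 2.0 and the power in each band is 0.484.
- The chance that the four bands do not all agree is 1 − 0.484⁴ − 0.516⁴ = 1 − 0.055 − 0.071 = 0.874.

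So with no age difference at all, a mixed pattern of significance appears 87% of the time. This bears directly on the planned analysis.

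**Step 2: a test of the age question, in bands or in years.** The plan proposes neither; this compares ways of adding one. Noncentrality is λ = N·R²/(1 − R²). For a linear relation R² = 0.09 when age is kept in years. With uniform ages, g equal bands keep 1 − 1/g² of that, and a cut with fraction p below it keeps 3p(1 − p). For a cut at 18, p = 11/53 = 0.208 and the fraction kept is 0.493.

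| Age term | R² | λ | df | Power |
|---|---|---|---|---|
| Linear | 0.0900 | 9.89 | 1 | about 87% |
| Linear plus curve | 0.0900 | 9.89 | 2 | about 80% |
| Median split | 0.0675 | 7.24 | 1 | about 76% |
| Quartile bands | 0.0844 | 9.22 | 3 | about 70% |
| Split at 18 | 0.0444 | 4.65 | 1 | about 57% |

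Simulation agrees to within about two points. At r = 0.25 the simulated figures are 72% (linear), 62% (linear plus curve), 59% (median split) and 42% (split at 18).

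With skewed ages (70% aged 7 to 23, the rest 23 to 60) and r = 0.275, a linear term has 80% power and banded tests have 52% to 56% (median split, tertiles, quartiles) or 51% (split at 18).

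**Step 3: open cut-points.** With no true age effect, a between-band test at a fixed cut at 18 rejects about 5% of the time. Taking the best of nine cuts (11.5, 12.5, 14, 16, 18, 21, 25, 30, 40) rejects about 21% of the time. The best of six (12, 18, 25, 30, 40, 50) rejects 18% to 20%.

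**Step 4: other shapes.** If the true relation is a step at 18 (r = 0.30, uniform ages), a split at 18 has about 86% power, linear plus curve about 64% to 66%, and linear alone about 57%. If the response rises to 18 and then levels off, the split at 18 has 71%, linear alone 48%, and linear plus curve 76% with a spline or about 65% with a quadratic.

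**The case against.** The strongest reply is that the power losses and the 21% figure describe a between-band comparison that section (9) never proposes. That is correct. A reader might infer that the planned analysis itself has 57% or 76% power for an age effect, or a 21% error rate. The documents do not support this: the planned tests do not compare ages, so neither figure is a property of the plan. Steps 2 and 3 only inform the choice of repair.

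A reader might also infer that the bands will be picked after the data are seen. The documents are silent. Section (6) mentions age groups in connection with recruitment, so bands may exist elsewhere. What stands is that none is prespecified here. The coding and blinding of demographic data in section (9) does not settle it, since age must be linked to the measurements for any age-specific analysis.

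Third, a reader might conclude that age in years always beats bands. Step 4 shows otherwise: a well-placed preset band does better if the relation is a step. With the curved term included, the gain over a median split under linearity and uniform ages is only 3 to 4 points.

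Finally, this is a small, single-visit, minimal-risk study with no declared primary hypothesis. That limits the consequence but does not supply the missing test, since the comparison of ages is an interest the protocol states itself.

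**Conclusion.** The concern holds in this form: the only planned test can use age solely through bands, no bands are defined, and a within-band test does not address whether the response differs by age. This needs no assumption beyond the wording of sections (3), (6) and (9). The 87% disagreement figure illustrates the risk of reading age effects from band-by-band significance; it assumes four independent bands of 25 and a common change of 0.4 SD.

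The advantage of age in years over bands is less certain. It is 80% against 57% to 76% for a linear relation with uniform ages and r = 0.30, and it can reverse for a step at a known age. The gap in the plan is established; the size of the benefit from this particular repair rests on assumed inputs.

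**What to change.** In section (9), regress each participant's change from baseline at each pressure on age in years, as a linear term plus one curved term whose form is written down in advance, and on sex. Test the age terms jointly and report the fitted relation with its confidence interval. State the significance level and how the repeated tests over pressures will be handled. A mixed model with age-by-pressure and sex-by-pressure terms and a participant random effect would cover all pressures in one analysis.

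Keep age bands for descriptive tables only, with cut-points fixed before the first measurement. If a child-versus-adult step is the expected shape, write that contrast in beforehand.

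The cost is analysis wording: no added participants, visits or measurements, and the regression runs in the planned SPSS package. The downside is that the curved term gives up some power if the relation is linear (about 87% to 80% in the illustration), and a smooth relation is assumed where a step may exist.
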